### **3.7.5.2 Clinical Global Impression - Severity**

The severity of illness for each subject will be rated using the CGI-S scale. To assess CGI-S, the rater or investigator will answer the following question: "Considering your total clinical experience with this particular population, how mentally ill is the subject at this time?" Response choices include: 0 = not assessed; 1 = normal, not ill at all; 2 = borderline mentally ill; 3 = mildly ill; 4 = moderately ill; 5 = markedly ill; 6 = severely ill; and 7 = among the most extremely ill subjects.

### **3.7.5.3 Clinical Global Impression - Improvement Scale**

The improvement of illness for each subject will be rated using the CGI-I scale. To assess CGI-I, the rater or investigator will rate the subject's total improvement whether or not it is due entirely to drug treatment. All responses will be compared with the subject's condition at baseline. Response choices include: 0 = not assessed, 1 = very much improved, 2 = much improved, 3 = minimally improved, 4 = no change, 5 = minimally worse, 6 = much worse, and 7 = very much worse. Direct entry of the CGI-I score on the eCRF without verifiable source documentation is not acceptable.

### **3.7.5.4 Subjective Well-being under Neuroleptic Treatment-Short Form**

The subject's feeling of their own well-being will be assessed using the 20-question SWN-S. The SWN-S is a validated self-report instrument to evaluate the subject's perception of well-being while receiving antipsychotic medication. Subjects will complete the questionnaire without discussing any of the items with others to avoid suggestive external manipulation. The questionnaire consists of 20 items and 5 subscales (mental functioning, social integration, emotional regulation, physical functioning, and self-control) whose items follow in random order. For items marked with a '+', response choices and scoring are as follows: not at all = 1, hardly at all = 2, a little = 3, somewhat = 4, much = 5, very much = 6. For items marked with a '-', the scoring is reversed; response choices and scoring are as follows: not at all = 6, hardly at all = 5, a little = 4, somewhat = 3, much = 2, very much = 1.

### **3.7.5.5 Montgomery-Asberg Depression Rating Scale**

The MADRS will be utilized as the primary assessment of a subject's level of depressive symptoms and must be administered using a structured interview guide. Detailed instructions for administration of the structured interview guide will be provided. This scale consists of 10 items, each with 7 defined grades of severity.

Protocol 031-201-00181

### 3.7.5.6 Young Mania Rating Scale

The YMRS consists of 11 items assessing the core symptoms of mania and is based on the subject's subjective report of his or her clinical condition. Additional information is based upon clinical observations made during the course of the clinical interview. Each item has 5 defined categories of severity with 4 items graded on a 0 to 8 scale (irritability, speech, content, and disruptive-aggressive behavior) and 7 items graded on a 0 to 4 scale.

### 3.7.5.7 Clinical Global Impression - Bipolar Version

The CGI-BP scale refers to the global impression of the subject with respect to bipolar I disorder. The scale rates the subject's severity of illness (CGI-BP-Severity: mania, depression, and overall bipolar illness) and change from preceding phase (CGI-BP change from preceding phase: mania, depression, and overall bipolar illness) based on a 7-point scale. Severity of illness (CGI-BP-Severity) should be rated at visits as indicated in the schedule of assessments (Table 3.7-1 for sparse sampling and Table 3.7-2 for robust sampling). At each visit other than Day 1 (baseline), the change from preceding phase (CGI-BP change from preceding phase) will be judged with respect to the subject's condition at baseline for that phase (ie, the last visit from the preceding phase).

## 3.7.6 Safety Assessments

### 3.7.6.1 Adverse Events

Refer to [Section 5](#) for the methods and timing for assessing, recording, and analyzing AEs.

### 3.7.6.2 Clinical Laboratory Assessments

The tests listed in [Table 3.7.6.2-1](#) will be collected at the time points presented in the schedule of assessments ([Table 3.7-1](#) for sparse sampling and [Table 3.7-2](#) for robust sampling) and processed in accordance with directions from the clinical chemistry laboratory.

Protocol 031-201-00181

**Table 3.7.6.2-1 Clinical Laboratory Assessments**

|  |  |
|--|--|
| Hematology:
Hematocrit
Hemoglobin
Platelet count
Red blood cell count
White blood cell count with differential

[REDACTED]   | Serum Chemistry:
Albumin
Alkaline phosphatase
ALT (or SGPT)
AST (or SGOT)
Bilirubin, total
Blood urea nitrogen
Calcium
Chloride
Cholesterol (total, low-density lipoprotein and high-density lipoprotein)
Creatine kinase
Creatinine
Gamma glutamyl transferase
Glucose
Lactate dehydrogenase
Magnesium
Phosphorus
Potassium
Protein, total
Sodium
Triglycerides
Uric acid |
| Urinalysis:
Appearance
Bilirubin
Color
Glucose
Ketones
Leukocytes
Nitrites
Occult blood
pH
Protein
Specific gravity
Urobilinogen
Microscopic analysis performed only if any part of the urinalysis is not negative | Drug Screen (all items in urine except where noted):
Alcohol (urine or breath)
Amphetamines
Barbiturates
Benzodiazepines
Cannabinoids
Cocaine
Marijuana
Methadone
Opiates
Phencyclidine
Propoxyphene   |

aPerimenopausal and postmenopausal female subjects only.

A pregnancy test will be conducted in females of childbearing potential (FOCBP) prior to trial intervention; results must be available prior to the administration of the IMP.

Additional pregnancy tests will be conducted throughout the trial at the time points presented in the schedule of assessments (Table 3.7-1 for sparse sampling and Table 3.7-2 for robust sampling).

A urine drug screen will be performed at screening and at check-in; however, additional urine drug screens can be performed at any time during the trial at the investigator's discretion (positive results are to be discussed with the medical monitor). A urine drug screen should also be performed if a subject experiences an SAE during the trial and the

Protocol 031-201-00181

urine drug screen will coincide with PK sampling following the occurrence of the SAE. The PK blood samples should be collected as early as is feasible to measure the plasma concentrations of aripiprazole.

Any value outside the normal range will be flagged for the attention of the investigator, who must indicate whether or not a flagged value is of clinical significance. If one or more values are questionable, the test(s) may be repeated. If the result of any test (or repeat test, if done) is indicated as clinically significant during the screening period, the subject will NOT be enrolled into the trial without the permission of the medical monitor. In addition, follow-up unscheduled labs should be performed on clinically significant abnormalities during the course of the trial. Unscheduled laboratory tests may be repeated at any time at the discretion of the investigator for appropriate medical care.

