**Day 29 ± 2 days (outpatient, all subjects)**

- Document birth control methods.
- Record concomitant medications and review for prohibited or restricted medications.
- Record adjustment of current oral antipsychotic, mood stabilizer, or antidepressant therapy.
- Assess and record AEs.
- Perform a urine pregnancy test (FOCBP only).
- Perform a physical examination.
- Measure weight.
- Take vital signs (systolic and diastolic blood pressure, heart rate, and body temperature).
- Administer a 12-lead safety ECG in triplicate (5 minutes apart).
- Collect clinical laboratory samples for hematology, clinical chemistry, prolactin assessment, and urinalysis.
- Administer the Since Last Visit version of the C-SSRS (predose).
- Assess EPS (SAS, AIMS, and BARS) (predose).
- Administer the PANSS (schizophrenia subjects only).
- Administer CGI-S scale and SWN-S (all subjects).
- Administer the MADRS, YMRS, and CGI-BP (bipolar subjects only).

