- Pregnancies are also defined as IREs. Although normal pregnancy is not an AE, it will mandate IMP discontinuation and must be reported on an IRE form to the sponsor. Pregnancy will only be documented on the AE eCRF if there is a complication or abnormality in the newborn.

Protocol 031-201-00181

**Clinical Laboratory Assessment Value Changes:** It is the investigator's responsibility to review the results of all laboratory tests as they become available. This review will be documented by the investigator's dated signature on the laboratory report. For each abnormal laboratory test result, the investigator needs to ascertain if this is an abnormal (ie, clinically relevant) change from baseline for that individual subject. This determination, however, does not necessarily need to be made the first time an abnormal value is observed. The investigator may repeat the laboratory test or request additional tests to verify the results of the original laboratory tests. If this laboratory value is considered clinically relevant by the investigator (eg, subject is symptomatic, requiring corrective treatment or further evaluation), or if the laboratory value leads to discontinuation, or fulfills a seriousness criterion, this is considered an AE.

**Severity:** Adverse events will be graded on a 3-point scale and reported as indicated on the eCRF. The intensity of an AE is defined as follows:

- 1 = Mild:** Discomfort noticed, but no disruption to daily activity.
- 2 = Moderate:** Discomfort sufficient to reduce or affect normal daily activity.
- 3 = Severe:** Inability to work or perform normal daily activity.

**IMP Causality:** Assessment of causal relationship of an AE to the use of IMP:

- Related:** There is a reasonable possibility of a temporal and causal relationship between the IMP and the AE.
- Not Related:** There is no temporal or reasonable relationship between the IMP and the AE.

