## 5.2 Trial Week Windows

The actual assessment date is mapped into the trial week. The definition of trial weeks for primary PK variables are described in [Table 5.2-1](#) and the definitions of trial weeks for efficacy scales and safety scales such as Extrapyramidal Symptoms (EPS) rating scales are included in [Table 5.2-2](#) and [Table 5.2-3](#). Trial days are derived from the formula: Trial Day = Date of assessment - Date of 1st IMP injection + 1. Based on the number of trial days, subjects are mapped to the corresponding trial week. For safety and efficacy variables, only the last observation within the same mapped trial week is used for imputing data on the following trial weeks in the derived last observation carried forward (LOCF) dataset. In addition, only last observations within the same mapped weeks are reported in the summary tables by trial week.

Table 5.2-1 Time Window for Trial Weeks for Primary PK Variables C28 and C56		
Scheduled Visit (Day)	Mapped Week (Trial Week)	Week Window (Trial Day Range ± 2 days)
197	28 (28 days after the 7th injection of 400 mg Abilify Maintena)	195-199
225	32 (28 days after the 8th injection of 400 mg Abilify Maintena or 56 days after the 4 th injection of 960 mg aripiprazole 2M LAI)	223-227

Table 5.2-2 Time Window for Mapping Trial Week for Efficacy Variables		
Scheduled Visit (Day)	Mapped Week (Trial Week)	Week Window (Trial Day Range)
1	Baseline	≤1 (before first IMP)
29	4	2-43
57	8	44-85
113	16	86-141
169	24	142-183
197	28	184-211
225	32	212-239

Protocol 031-201-00181

Table 5.2-3 Time Window for Mapping Trial Week for Safety Variables		
Scheduled Visit (Day)	Mapped Week (Trial Week)	Week Window (Trial Day Range)
1	Baseline	≤1 (before first IMP)
8	1	2-11
15	2	12-18
22	3	19-25
29	4	26-43
57	8	44-71
85	12	72-99
113	16	100-127
141	20	128-155
169	24	156-183
197	28	184-211
225	32	212-239

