### 8.5 Clinical Laboratory

Clinical laboratory tests include serum chemistry, hematology, urinalyses and other lab analyses. Potentially clinically relevant laboratory test abnormalities will be listed by subject and by test. Criteria for potentially clinically relevant laboratory test abnormalities are provided in [Appendix 2](#). Subjects with aspartate aminotransferase (AST) or alanine aminotransferase (ALT)  $\geq$  3 x upper limit of normal value and total bilirubin  $\geq$  2 x upper limit of normal value will be listed. The incidences of potentially clinically relevant laboratory tests abnormalities based on observations during scheduled and unscheduled post-baseline visits will be tabulated by treatment formulation and disease type. Summary statistics for clinical laboratory measurements and changes from baseline will be presented by trial visit, treatment formulation and disease type.

If laboratory tests assessments are repeated for the same mapped trial visit, the last repeated values will be used for summary tables. This is accomplished by sorting patient data by visit date and visit time (if applicable) within the same trial visit. If the lab data are recorded as ranges (i.e., including < or > limit of quantification), these data are not

Protocol 031-201-00181

included in the calculations for changes from baseline but included in the calculations for incidences.

The incidence of prolactin level above the upper limit of normal range (potentially clinically relevant change) will be calculated by treatment formulation and disease type. Summary statistics (mean, standard deviation, median, minimum, and maximum) and changes from baseline in prolactin concentration will be presented by trial visit, treatment formulation and disease type. Similar analyses will be performed for male and female, respectively. Additionally, incidences of treatment-emergent relevant changes in lipid parameters and glucose (as defined in [Table 8.5-1](#)) will be summarized by treatment formulation and disease type, though those blood samples are not required to be collected at the fasted state.

Table 8.5-1 Criteria for Treatment-emergent Relevant Changes in Lipids Parameters and Glucose		
Parameters	Baseline	Any Post-baseline
Total Cholesterol (mg/dL)		
	Normal <200	High $\geq$ 240
	Borderline 200~<240	High $\geq$ 240
	Normal/Borderline <240	High $\geq$ 240
	Normal <200	Borderline/High $\geq$ 200
	Any Value	Increased $\geq$ 40
LDL Cholesterol (mg/dL)		

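### Laboratory repeats are largely prompted by abnormal values, and the SAP's last-value rule can let them replace the scheduled result in by-visit mean changes

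*Protocol*

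**What the plan says.** **When tests are repeated.** Protocol Section 3.7.6.2 gives three routes to an extra laboratory test.

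- A doubtful result: "If one or more values are questionable, the test(s) may be repeated".
- A clinically significant on-trial abnormality: "In addition, follow-up unscheduled labs should be performed on clinically significant abnormalities during the course of the trial".
- General discretion: "Unscheduled laboratory tests may be repeated at any time at the discretion of the investigator for appropriate medical care".

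Protocol Section 5.1, on abnormal results, adds: "The investigator may repeat the laboratory test or request additional tests to verify the results of the original laboratory tests".

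**When tests are scheduled.** After baseline, laboratory samples are due at two visits. At Day 29 the instruction is: "Collect clinical laboratory samples for hematology, clinical chemistry, prolactin assessment, and urinalysis". At Day 225 or early termination the same panels are drawn, without prolactin.

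**Which value is reported.** SAP Section 8.5: "If laboratory tests assessments are repeated for the same mapped trial visit, the last repeated values will be used for summary tables". The selection is made by sorting on visit date and time. SAP Section 5.2 has the same general rule: "only last observations within the same mapped weeks are reported in the summary tables by trial week". In SAP Table 5.2-3, Week 4 covers Days 26-43 and Week 32 covers Days 212-239.

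**Where it is used.** Protocol Section 7.4.1 lists mean change from baseline in laboratory values, by visit, treatment group and disease type, among the primary endpoint analyses. Incidences of abnormal values work differently. Under SAP Sections 8 and 8.5 they count any subject with at least one abnormality, from scheduled and unscheduled post-baseline visits, and abnormal values are listed by subject and test.

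**The concern.** A normal scheduled value usually stands as measured. An abnormal one is more likely to be followed by a second draw, and if that draw falls in the same window the SAP reports it instead. The second value will tend to lie closer to normal, because of regression to the mean, recovery or treatment. Which number enters the mean thus depends on the outcome itself.

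At stake is the accuracy of the by-visit laboratory means and changes from baseline, which the protocol places among its primary safety summaries. The expected direction is toward normal. Prolactin is the most exposed analyte: Day 29 is its only scheduled post-baseline draw, so no later scheduled result can offset a replaced one.

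**Working it through.** The documents state no figure for laboratory repeats, so there is nothing to reproduce. The check has two parts: whether replacement can occur under the rules, and how large its effect could be under stated assumptions.

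**Step 1. Windows (SAP Table 5.2-3).**

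| Scheduled draw | Window | Days after the draw in which a recheck replaces it |
|---|---|---|
| Day 29 | 26-43 | 43 - 29 = 14 |
| Day 225 | 212-239 | 239 - 225 = 14 |

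A recheck on Day 44 or later maps to Week 8 or beyond and leaves the Week 4 value in place. This reading takes unscheduled results to be eligible for the mapped visit. SAP Section 8.5 does not say so outright, but it refers to the mapped visit, sorts by date and makes no exception for them.

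**Step 2. Model (assumptions, not document figures).** Let the scheduled value be Y ~ N(d, 1) in baseline SD units, with d the true shift of the arm. Suppose Y is replaced by a recheck whenever Y > c. The recheck has the same true mean and correlates r with Y, so its expectation given Y is d + r(Y - d). Then

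bias of the reported mean = -(1 - r) × E[(Y - d) 1(Y > c)] = -(1 - r) × φ(c - d),

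where φ is the standard normal density.

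**Step 3. Upper-end case.** Every value above the baseline 95th percentile is rechecked within the window: c = 1.645. In an arm with d = 0.5 that is P(Z > 1.145), about 12.6% of subjects.

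| r | Arm with d = 0.5: -(1 - r) φ(1.145) | Arm with d = 0: -(1 - r) φ(1.645) | Understatement of the contrast |
|---|---|---|---|
| 0.5 | -0.104 | -0.052 | 0.104 - 0.052 = 0.052 |
| 0.8 | -0.041 | -0.021 | 0.041 - 0.021 = 0.021 |

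A true rise of 0.5 SD would be reported as about 0.40 SD (r = 0.5) or 0.46 SD (r = 0.8).

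**Step 4. Lower-end case.** Only the top 1% of the baseline distribution is rechecked.

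| r | Arm with d = 0.5 | Arm with d = 0 | Understatement of the contrast |
|---|---|---|---|
| 0.5 | -0.038 | -0.013 | 0.024 |
| 0.8 | -0.015 | -0.005 | 0.010 |

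**Step 5. Baseline.** The within-arm figures assume baseline is not replaced. SAP Section 5.1 defines baseline as the last evaluable assessment before injection, and the Day 1 samples are drawn predose on the dosing day. A recheck prompted by a Day 1 result would usually come after dosing and could not become the baseline.

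**Limits of the model.** At r = 1 (the abnormality persists unchanged) the bias is zero. If the recheck follows recovery or treatment, the loss exceeds the formula.

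**The case against.** Several points against the concern stand.

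- **Repeats are not confined to abnormal values.** A reader might infer that tests are repeated only when a value is questionable or clinically significant. Section 3.7.6.2 contradicts this with its discretionary route, and repeating a questionable value, or repeating an abnormal one to verify it, is optional.
- **Replacement is conditional.** A reader might also infer that abnormal values necessarily drop out. A recheck has to be done, fall in the same window and differ from the original. No rechecks are scheduled after Day 225, so the effect may fall mainly on Week 4.
- **The abnormality is not lost to the safety analysis.** Incidence counts and listings keep it, and a value the investigator considers clinically relevant becomes an adverse event under Protocol Section 5.1. A by-visit mean and an any-time incidence measure different things, so a difference between them is not in itself a contradiction.
- **The effect is small against sampling error.** With 129 subjects per arm and a change SD of 1, the standard error of an arm mean is 1/√129 = 0.09 SD. The upper-end bias of 0.10 SD is about one standard error, and the contrast figures lie well below that. These tables are descriptive, with no decision threshold.
- **A repeat may be the better measurement.** The rule is prespecified and the same in both arms, and a recheck of a doubtful value can be the more reliable result.

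A further tempting inference concerns the arms. The 400 mg arm is dosed again on Day 29 and the 960 mg arm is not, so a Day 30-43 recheck follows a new injection in one arm only. The documents give neither a direction nor a size for any resulting difference, so no bias between arms is claimed on that ground.

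These points limit the size and certainty of the concern. They do not remove the fact that replacement depends largely on the result.

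**Conclusion.** The concern holds in a limited form. Laboratory repeats are largely, though not only, prompted by questionable or clinically significant values. The last-value rule can let them replace the scheduled result for up to 14 days after Day 29 or Day 225. This pulls the by-visit means and changes from baseline toward normal, while incidence tables, listings and adverse events are unaffected.

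The size cannot be established, because no repeat frequency is given. With all values above the baseline 95th percentile rechecked and a correlation of 0.8 to 0.5, a true 0.5 SD rise is understated by about 0.04 to 0.10 SD. An unshifted arm moves by about -0.02 to -0.05 SD. The 0.02 to 0.05 SD contrast figure (4% to 10% of 0.5 SD) should not be read as the error in a within-arm change: that would require baseline values to be replaced in the same way, which the baseline definition makes unlikely.

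This is a modest, avoidable bias in a primary safety summary. It is worth correcting because correction is cheap.

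**What to change.** In SAP Section 8.5, and in the matching sentence of Section 5.2, state three things:

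- By-visit laboratory means and changes from baseline use the scheduled-visit (first valid) result.
- A repeat replaces that result only when the original sample is documented as invalid.
- Value-triggered repeats and unscheduled follow-up results enter only the incidence tables and listings.

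Consider the same wording for vital signs (SAP Section 8.3) and ECGs (SAP Section 8.6), which also take the last repeat. For ECGs, Protocol Section 3.7.6.4 calls for a repeat when a result is considered clinically significant.

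The cost is one sentence in the SAP and a selection flag in the laboratory dataset. No new data are needed, and nothing changes in when tests are repeated. The downside is that some doubtful originals that were never invalidated stay in the means. A sensitivity summary using the last repeat would show how much that matters.

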### **3.7.6.3 Physical Examination and Vital Sign Assessments**

Complete physical examinations will be performed at the time points presented in the schedule of assessments ([Table 3.7-1](#) for sparse sampling and [Table 3.7-2](#) for robust sampling). The principal investigators or designees are primarily responsible for performing the physical examination. Whenever possible, the same individual should perform all physical examinations for any individual subject. If the appointed designee is to perform the physical examination, he/she must be permitted by local regulations and his/her name must be included on the FDA Form 1572 as principal investigator or sub-investigator and must be listed on the trial site delegation of authority form as performing this function. Any clinically significant condition present at a post-treatment physical examination that was not present at the baseline physical examination should be documented as an AE and followed to a satisfactory conclusion.

Body height and weight will also be measured during screening for calculation of body mass index (BMI) and weight will be measured as part of all subsequent physical examinations. For the measurement of height, the measurement will be made without shoes. For the measurement of weight, all efforts will be made to use the same scale for all measurements throughout the trial.

Vital signs will be taken at the time points presented in the schedule of assessments ([Table 3.7-1](#) for sparse sampling and [Table 3.7-2](#) for robust sampling). Vital signs will be obtained prior to PK blood draws and ECGs at the nominal time points, where applicable. Vital signs will include systolic and diastolic blood pressure, heart rate, and body temperature. At each time point for vital signs, blood pressure (systolic and diastolic) and heart rate will be taken after subjects have been in the supine position for at least 5 minutes and again after subjects have been standing for 2 minutes, but not more than

Protocol 031-201-00181

3 minutes. Body temperature will be taken with the subject in the supine position (ie, only once).

